1.4 Summary of Clinical Experience

As of 25Aug2015 (cutoff date for D5100C00001 Cohort 6 interim analysis), a total of 46 healthy volunteers have received single IV doses of MEDI4920 over the dose range 3 mg to 1000 mg in Study D5100C00001.

Study D5100C00001 is a Phase 1, randomized, blinded, placebo-controlled, single ascending dose (SAD) study to evaluate the safety and tolerability of single-ascending IV doses of MEDI4920 in healthy adult male subjects and healthy adult female subjects of non-childbearing potential. In addition to assessing safety and tolerability, the study also characterized the PK of MEDI4920, assessed anti-drug antibody (ADA) to MEDI4920, and evaluated the effect of MEDI4920 on TDAR after administration of the KLH antigen. The study was conducted at one site in the United Kingdom. A total of up to 56 subjects were planned for randomization within this study: 3 subjects were randomized in a 2:1 ratio for each of Cohorts 1 and 2 (3 and 10 mg MEDI4920, respectively or placebo) and 10 subjects each randomized in a 4:1 ratio for Cohorts 3 to 7 (30, 100, 300, 1000, and 3000 mg MEDI4920, respectively, or placebo).

When all subjects in Cohort 5 completed Day 43 assessments, a first interim analysis was conducted to evaluate the safety and tolerability of MEDI4920, PK, ADA, and the level of inhibition of the TDAR in Cohorts 1-5. With respect to safety, there were no withdrawals from the study, and one serious adverse event (SAE) of fractured tibia was reported in the placebo arm. Adverse events (AEs) were generally minor and balanced across placebo and MEDI4920 dose groups. One case of herpes zoster reactivation (shingles) was reported in the

30 mg dose group (Grade 2, start date Day 79). There were no deaths, no reports of thromboembolic events, no severe hypersensitivity or severe infection events, and no concerns from the laboratory assessment of platelet function and coagulation. PK parameters (C_{max} and AUC) increased in a dose-proportional fashion, with a half-life of approximately 8 days for the 300 mg IV dose. Between 50% to 100% of subjects in Cohorts 1 to 4 developed ADAs at at least one time point after dosing, whereas only 3 of 8 subjects in Cohort 5 developed ADAs after dosing. The ADA positive subjects had faster clearance and reduced observed MEDI4920 exposure. According to the pre-specified dose escalation criteria, as TDAR inhibition was < 75% vs placebo and no safety concerns were observed, Cohort 6 (1000 mg dose) was initiated. An additional 10 subjects were randomized in a 4:1 ratio to receive either 1000 mg MEDI4920 or placebo.

When all subjects in Cohort 6 completed Day 43 assessments, a second interim analysis was conducted to evaluate the safety and tolerability of MEDI4920, PK, ADA, and the level of inhibition of the TDAR in Cohorts 1-6, in order to evaluate the requirement for Cohort 7 (3000 mg). The safety profile remained consistent with the safety profile observed at the first interim analysis, with no deaths, serious or severe AEs, thromboembolic events, severe hypersensitivity or severe infection events, and no concerns from the laboratory assessment of platelet function and coagulation. No subjects in Cohort 6 (1000 mg) were positive for ADAs up to Day 29, which was the last available ADA time point in Cohort 6 prior to interim assessments.

After the second interim analysis, TDAR inhibition was observed in a dose-dependent manner. A dose response analysis at Day 43 of the dose cohorts up to and including 1000 mg demonstrated a statistically significant linear dose response (p = 0.003) with the 1000 mg dose observing a 77% inhibition of the TDAR IgG response compared to placebo (95% confidence intervals [CIs]: 41%, 91%).

1.5 Rationale for Conducting the Study

MEDI4920 is being developed for the treatment of B-cell dependent autoimmune diseases.

The current study is designed to characterize the safety, tolerability, PK, biomarkers, immunogenicity, and clinical response of multiple doses of MEDI4920 in subjects with moderate to severe RA.

The results from this study will form the basis for decisions regarding appropriate repeat dosing strategies of MEDI4920 for future studies in subjects with RA and/or other autoimmune conditions.

1.6 Potential Risks

The study will be performed in accordance with ethical principles that have their origin in the Declaration of Helsinki and are consistent with International Conference on Harmonisation (ICH)/Good Clinical Practice (GCP), and applicable regulatory requirements.

Based on clinical data from Cohorts 1-6 of the SAD study, there are no identified risks for humans associated with MEDI4920. Potential risks based on the mechanism of action (MOA) of MEDI4920 and mitigation plans included in the protocol are summarized below.

Anaphylaxis and Serious Hypersensitivity Reactions

No severe or serious hypersensitivity reactions have been observed with MEDI4920 at doses up to 1000 mg in the SAD study.

In the current study, subjects will be excluded from participation if they have had a history of a severe allergic reaction to any component of the investigational product formulation or to any other biologic therapy. The risk of hypersensitivity reactions is considered maximal after the first two IV administrations of MEDI4920 (Days 1 and 15). To monitor for infusion and/or hypersensitivity reactions, subjects will be in a clinical trial facility and closely monitored for 4 hours after the end of the infusion for the first two doses (Days 1 and 15). Doses will be administered by IV infusion over minimum times of 30 minutes for the 75 mg dose, 60 minutes for the 500 mg dose, 90 minutes for the 1000 mg dose, and 90 minutes for the 1500 mg dose. The infusion will be discontinued if there is evidence of infusion reaction and supportive treatment may be instituted. Guidelines for monitoring relevant AEs encompassing hypersensitivity, angioedema and anaphylaxis and for managing acute anaphylactic shock and minor allergic episodes will be in place at investigational sites. Study sites will include facilities and expertise for emergency care/resuscitation, including access to hospital and intensive care unit.

Serious and/or Opportunistic Infections

No severe or serious infections have been observed in the first time in human (FTIH) SAD study. One case of herpes zoster reactivation was reported in a subject receiving 30 mg MEDI4920.

Weekly IV administration of 150 or 300 mg/kg MEDI4920 to sexually mature cynomolgus monkeys for 6 months resulted in an opportunistic fungal infection in one animal treated with MEDI4920 300 mg/kg IV, and changes suggesting potential systemic infection were observed in another animal treated with MEDI4920 150 mg/kg (see Section 1.3).

Measures taken in the current study to minimize the risk of immunosuppression-related infections include the following:

- During screening, subjects will be excluded from the study if they have had a recent (within 12 months) or active hepatitis A infection; if they test positive or have been treated for hepatitis B, hepatitis C, or human immunodeficiency virus (HIV) infection; if they have evidence of active or untreated latent tuberculosis (TB); if they have a recent history (last 12 months) of recurrent herpes zoster and/or opportunistic infection; and/or if they are taking immunosuppressant medication (see exclusion criteria in Section 4.1.3 and prohibited concomitant medications in Section 4.7.2).
- Subjects will not be allowed to receive live (attenuated) vaccine within the 4 weeks prior to dosing or during the study until the end of follow-up.
- Clinical assessments for signs of infection will be performed at each study visit. Subjects will be given instructions on potential signs of infection and instructed to contact investigator if they have signs or symptoms of an infection. Blood samples for serology and viral polymerase chain reaction (PCR) will be collected at screening and stored to assess new vs reactivation of Epstein-Barr virus (EBV) and cytomegalovirus (CMV) in case an EBV or CMV infection is reported as an AE during the study.

Unknown Consequences of Exposure in Utero

No embryo-fetal studies have been conducted to date.

This study requires all female subjects of childbearing potential to use at least one highly effective method of contraception from the time of screening up through at least 6 months after the final dose of investigational product. The acceptable methods of contraception are described in Section 4.1.2.

In addition, the investigator must inform the subjects about the risks involved with some of the background medications used in RA and accepted in the current study (eg, MTX or leflunomide) as these agents are known to have potential deleterious effects on conception, pregnancy and fetal health (see Section 4.1.2).

The requirement for adherence with contraceptive guidance in the protocol and screening for pregnancy (serum or urine) will be monitored throughout the duration of the study.

Thrombotic and Embolic Events

Previous clinical trials with anti-CD40L mAbs that were Fc enabled demonstrated increased incidence of thromboembolic events, and subsequent nonclinical studies identified that platelet activation due to binding of Fc receptor by immune complex of anti-CD40L and

soluble CD40L was the likely mechanism underlying the association between anti-CD40L exposure and thrombosis. MEDI4920 was engineered to lack Fc fragment.

No thromboembolic events have been reported in animal studies and in the human SAD study with MEDI4920.

To minimize the risk of thromboembolic events in the current study, subjects will be excluded from participation if they have a medical history of confirmed venous thromboembolism or arterial thrombosis or if they have significant clinical and molecular risk factors for thromboembolic events or arterial thrombosis. In addition, any subjects with a clinically significant abnormal coagulation panel at screening will be excluded from this study (see Section 4.1.3).

Thromboembolic events will be monitored by AE evaluation and physical examinations performed during the study. If a subject dosed with MEDI4920 experiences a confirmed or suspected thromboembolic event during the evaluation period or follow-up period, the dose escalation will be suspended and the event will be fully evaluated (see Section 3.1.3 for additional details).

Immune Complex Disease

The potential risk of immune complex disease is based on the potential risk known to be associated with foreign proteins and mAbs. The occurrence of ADA could result in immune complex disease (with manifestations such as arthralgia, serum-sickness, nephritis, and vasculitis) or altered MEDI4920 levels or activity. Subjects in clinical studies with MEDI4920 will be monitored for the presence of ADA and for clinical manifestations that may be associated with the formation of specific antibodies to MEDI4920.

1.7 Research Hypotheses

1.7.1 Primary Hypothesis

The primary hypothesis is that multiple ascending IV doses up to 1500 mg of MEDI4920 once every 2 weeks (Q2W) over a 12-week period will be safe and well-tolerated in subjects with RA when compared with placebo in combination with MTX or another cDMARD.

1.7.2 Secondary Hypothesis

A secondary hypothesis has not been established for this study.

1.7.3 Exploratory Hypotheses

The exploratory hypotheses are that CCI
CCI
CCI
CCI
CCI

2 OBJECTIVES AND ENDPOINTS

2.1 Objectives

2.1.1 **Primary Objective**

To assess the safety and tolerability of multiple ascending IV doses of MEDI4920 in subjects with adult-onset RA.

2.1.2 Secondary Objectives

To evaluate the PK and immunogenicity of MEDI4920 in subjects with adult-onset RA.

2.1.3 Exploratory Objectives

2.2 Study Endpoints

2.2.1 **Primary Endpoints**

- 1. The incidence of AEs and SAEs.
- 2. The incidence of treatment-emergent AEs of special interest (AESIs) as follows:
 - Thrombotic and embolic events
 - Hepatic function abnormality (meeting the definition of Hy's Law [HL]; see Section 5.6.2)
 - Anaphylaxis and serious hypersensitivity reactions
 - Infusion-related reactions

- Immune complex disease
- Serious and/or opportunistic infections (including but not limited to reactivation of latent viral infection [varicella zoster (VZ), herpes simplex virus (HSV), EBV, CMV] and TB)
- 3. Vital signs, laboratory parameters (including coagulation parameters), electrocardiograms (ECGs), and physical examinations.

2.2.2 Secondary Endpoints

The PK profile, PK parameters, and immunogenicity of MEDI4920 will be assessed for each cohort

2.2.3 Exploratory Endpoints

3 STUDY DESIGN

3.1 Description of Study

3.1.1 Overview

This is a multicenter, randomized, double-blind (investigator, subject, and sponsor will be blinded to treatment assignment), placebo-controlled study to evaluate the safety and tolerability of multiple ascending doses (MADs) of MEDI4920 in subjects with adult-onset RA (moderate to severe, as defined by DAS28 CRP \geq 3.2 at screening) with an inadequate response to MTX or other cDMARDs or a biologic anti-TNF α agent.

The study is planned to be conducted at approximately 15 sites in 2 to 4 countries. A maximum of 54 eligible subjects are planned for this study. Approximately 40 subjects will be randomized in 3 cohorts to receive either 75 mg (Cohort 1), 500 mg (Cohort 2), or 1500 mg (Cohort 3) MEDI4920, or placebo once Q2W in combination with MTX or another cDMARD for up to 12 weeks.

An additional 14 subjects will be randomized in a 5:2 ratio to an additional cohort (Cohort 4), to better characterize the dose (exposure) - response relationship. The selected dose of MEDI4920 in Cohort 4 is 1000 mg Q2W.

Subjects will undergo a screening period of up to 6 weeks followed by randomization and treatment for 12 weeks. Subjects will be followed for an additional 12 weeks after the treatment period for safety. Each subject will participate in the study for up to approximately 30 weeks (includes a 6-week screening period, a 12-week treatment period, and a 12-week follow-up period).

Subjects will receive an IV dose of MEDI4920 or placebo Q2W for up to 12 weeks as follows:

- Cohort 1: 75 mg MEDI4920 (N = 8) or placebo (N = 2) as a single IV dose administered over at least 30 minutes Q2W
- Cohort 2: 500 mg MEDI4920 (N = 10) or placebo (N = 4) as a single IV dose administered over at least 60 minutes Q2W
- Cohort 3: 1500 mg MEDI4920 (N = 12) or placebo (N = 4) as a single IV dose administered over at least 90 minutes Q2W
- Cohort 4: 1000 mg MEDI4920 (N = 10) or placebo (N = 4) as a single IV dose (administered over at least 90 minutes Q2W)

Subjects will be administered investigational product via IV infusion using an infusion pump.

All subjects will receive a total of 7 doses of investigational product (MEDI4920 or placebo) during the 12-week treatment period. Details about dose escalation can be found in Section 3.1.3.

A screening visit(s) will be performed within 6 weeks (42 days) prior to dosing. All subjects will receive investigational product on the morning of Day 1. An overnight stay on Day -1 prior to administration of investigational product on Day 1 is recommended but not mandatory. If no safety concerns are identified, subjects will be discharged from the study site on Day 2 (end of the inpatient treatment period) after all study procedures have been completed. Subjects in all cohorts will return to the study site Q2W (Days 8, 15, 29, 43, 57, 71, and 85) for investigational product administration and/or specific assessments and blood draws, as indicated in Table 4.2.2-1.

During the treatment period, assessments of RA parameters as well as evaluations of safety, tolerability, PK, and immunogenicity of MEDI4920 will be performed at the time points indicated in Table 4.2.2-1.

Following the final IV infusion of investigational product, subjects will return to the study site for follow-up visits beginning at Week 13 (Day 92) and continuing through Week 24

(Day 169) to evaluate safety, tolerability, PK and ADA of MEDI4920 as indicated in Table 4.2.3-1.

A study flow diagram is presented in Figure 3.1.1-1.

Figure 3.1.1-1 Study Flow Diagram

Ab = antibody; ADA = anti-drug antibody; D = day; IV = intravenous; PK = pharmacokinetic; Q2W = once every 2 weeks

The endpoints to be measured in this study are described in Section 2.2.

3.1.2 Treatment Regimen

A maximum of 54 subjects will be randomized in a 4:1 ratio (Cohort 1), in a 5:2 ratio (Cohort 2), in a 3:1 ratio (Cohort 3), and in a 5:2 ratio (Cohort 4) to receive either MEDI4920 or placebo as described in Table 3.1.2-1:

Cohort	N (active:placebo)	Dose	Treatment Regimen ^a
1	4:1	75 mg	Single IV dose infused over at least 30 minutes on Days 1, 15, 29, 43, 57, 71, and 85
2	5:2	500 mg	Single IV dose infused over at least 60 minutes on Days 1, 15, 29, 43, 57, 71, and 85
3	3:1	1500 mg	Single IV dose infused over at least 90 minutes on Days 1, 15, 29, 43, 57, 71, and 85
4	5:2	1000 mg	Single IV dose infused over at least 90 minutes on Days 1, 15, 29, 43, 57, 71, and 85

Table 3.1.2-1 Investigational Product Dose and Treatment Regimen

IV = intravenous; TBD = to be determined.

^a For Cohorts 1-4, investigational product will be administered via IV infusion using an IV infusion pump.

The timing of administration of investigational product will be staggered within each cohort to allow for review of safety and tolerability data from the first group of subjects before progression to the next group of subjects.

3.1.3 Dose Escalation and Cohort Progression

Cohorts 1 to 3 will start sequentially, with escalation from Cohort 1 to Cohort 2 and Cohort 2 to Cohort 3 confirmed by a Dose Escalation Committee (DEC) comprised of MedImmune study team members and the Study Global Chief Investigator, who will assess in a blinded fashion the safety/tolerability data after the last subject in a cohort completes Day 29 (Week 4) of treatment and has AE/safety laboratory data available at that time point. There will be a total of three DEC meetings during the study; the first DEC meeting will only review data from Cohort 1 whereas the second DEC meeting will review cumulative safety data from first two dose cohorts being tested to date. The third DEC meeting will constitute a thorough evaluation of the cumulative safety and tolerability data for Cohorts 1 and 2 in addition to the data up to Day 85 for Cohort 3. While this review will not pertain to a dose escalation, it will contribute to the decision to instigate Cohort 4 (see below).

After the last Cohort 3 subject completes the Day 85 (Week 12) assessments, the primary analysis will be conducted to include safety, tolerability, PK, ADA, biomarker, and clinical response. Based on the outcome of this analysis, a fourth cohort will be included to better understand the dose (exposure)-response relationship.

If one or more of the following criteria are met, dose escalation will be suspended and the event(s) will be fully evaluated:

- A subject dosed with MEDI4920 experiences a confirmed or suspected thromboembolic event during the evaluation period or follow-up period. If the thromboembolic event is initially reported as "suspected", because of the unavailability of sufficient information to support a definitive diagnosis at that time, the DEC will re-assess the event when complete clinical/laboratory information is provided by the study site. A diagnosis algorithm (adapted from Wells and Anderson, 2013; Section 10.5 [Appendix 5]), is recommended to be used for any case of suspected DVT or PE. This includes clinical pre-test probability, D-dimer, and available imaging results. Based on full evaluation of the data as well as the diagnosis algorithm, if a thromboembolic event is ruled out or considered unlikely, dose escalation can be resumed.
- At least 2 subjects dosed with MEDI4920 in a single cohort experience either Grade 3 or higher treatment-emergent AEs (TEAEs) of the same type (excluding rheumatoid joint flares) or any SAE.
- At least 2 subjects dosed with MEDI4920 in a single cohort experience serious infections.
- In addition to the above criteria, the DEC may recommend stopping dose escalation and further evaluation of any significant medical event(s) or confirmed clinically significant laboratory abnormalities (including coagulation tests) that are considered related to investigational product.

If the DEC suspends the dose escalation and subsequently decides to resume dosing at the same or higher doses, approval from the relevant regulatory authorities and Independent Ethics Committees (IECs) will be obtained prior to dosing.

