- 6. Section 4.3.2 (Clinical Laboratory Tests): Corrected a typographical error by changing the abbreviation for total bilirubin from "TLB" to "TBL".
- 7. Section 4.5.1.5 (Preparation of Intravenous Dose): Added sub-headings to clearly differentiate between the MEDI4920 and placebo dose preparation steps; relocated the following sentence "A vial should be used only one time to prepare a single dose" to the MEDI4920 sub-section for clarification as no vials are used for the placebo treatment.

Protocol Amendment 1, 05Apr2016

Text revisions resulting from this amendment are incorporated in the body of Protocol Amendment 1. Main changes to the protocol are summarized below.

- Protocol Synopsis, Section 2.2.1 (Primary Endpoints): Revised wording for AESIs to be consistent with the standard potential risks language used in other clinical programs in MedImmune/AstraZeneca and in other MEDI4920 regulatory documents; added additional language for serious and/or opportunistic infections to clarify that the evaluations are not limited to just VZ, HSV, EBV, EMV, and TB. These changes will not affect the actual endpoints that are planned to be evaluated in the study or the safety monitoring of these events.
- 2. Section 1.6 (Potential Risks): Revised wording pertaining to the potential risks associated with MEDI4920 for consistency with the aforementioned changes in the AESI language; based on recommendations from the United States Food and Drug Administration (US FDA), the language pertaining to thromboembolic events was modified by adding the phrase "or suspected" such that dose escalation will be suspended even in the case of a suspected thromboembolic event, until additional data allow an informed diagnosis of the event to be made.
- 3. Section 3.1.1 (Overview); Section 6.2 (Monitoring of the Study): Changed the term "study drug" to "investigational product" for consistency with wording in the protocol.

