10.5 Appendix 5 – Diagnosis of a Potential Thromboembolic Event

10.5.1 Clinical Probability Score of Deep Vein Thrombosis - Wells Criteria

DVT: Wells	
Variable	Points
Active cancer (treatment ongoing or within previous 6 mo or palliative)	1
Paralysis, paresis, or recent plaster immobilization of the lower extremities	1
Recently bedridden for more than 3 d or major surgery within 4 wk	1
Localized tenderness along distribution of the deep venous system	1
Entire leg swollen	1
Calf swelling by more than 3 cm compared with asymptomatic leg (measured 10 cm below tibial tuberosity)	1
Pitting edema (greater in the symptomatic leg)	1
Collateral superficial veins (nonvaricose)	1
Past history of DVT	1
Alternative diagnosis as likely or greater than that of DVT	-2

d = days; DVT = deep vein thrombosis; mo = months; wk = weeks Score $\leq 1 =$ DVT is clinically unlikely; Score $\geq 2 =$ DVT is clinically likely

Algorithm for Suspected Deep Vein Thrombosis

In every case of a clinically suspected deep vein thrombosis (DVT), the clinical probability score must be calculated using by the aforementioned Wells criteria and a D-dimer test must be performed.

- If clinical probability shows "DVT unlikely" (ie, score ≤ 1), and D-dimer value is ≤ ULN, DVT is excluded.
- If clinical probability shows "DVT unlikely" (ie, score ≤ 1), and D-dimer value is > ULN, compression ultrasound will be performed.
 - If ultrasound shows no abnormal changes, DVT is excluded.
 - If ultrasound shows abnormal changes, compatible with thrombosis, DVT is confirmed.
 - If ultrasound is unavailable/equivocal and D-dimer is only increased at the time of event, DVT is considered "likely".
- If clinical probability shows "DVT likely" (ie, score ≥ 2), compression ultrasound will be performed irrespective the D-dimer value.
 - If ultrasound shows no abnormal changes, ultrasound should be repeated within 7 days; if ultrasound again shows no abnormal changes, DVT is excluded.

- If ultrasound shows abnormal changes compatible with thrombosis, DVT is confirmed.
- If ultrasound is unavailable or equivocal, DVT is considered "likely".
- Each situation that cannot be adjudicated using the algorithm above will be considered as "DVT likely" and dose escalation will be suspended.

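### If a safety criterion is met in Cohort 4, the protocol orders no pause of randomization or dosing, because the only restraint in Section 3.1.3 is suspension of dose escalation

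*Protocol*

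**What the plan says.** Protocol 3.1.3 gives three event criteria: a confirmed or suspected thromboembolic event in one MEDI4920 subject; two MEDI4920 subjects in one cohort with Grade 3 or higher events of the same type or with any SAE; and two MEDI4920 subjects in one cohort with serious infections. A fourth item lets the DEC recommend stopping escalation for other significant events. The stated consequence is: "If one or more of the following criteria are met, dose escalation will be suspended and the event(s) will be fully evaluated".

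Section 1.6 repeats it for thromboembolic events ("the dose escalation will be suspended and the event will be fully evaluated"), and the last bullets of 10.5.1 and 10.5.2 do so for events that the diagnostic algorithm cannot settle ("dose escalation will be suspended").

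The escalation steps are named in 3.1.3: "with escalation from Cohort 1 to Cohort 2 and Cohort 2 to Cohort 3 confirmed by a Dose Escalation Committee (DEC". The same section fixes the committee's schedule: "There will be a total of three DEC meetings during the study". The third meeting covers Cohort 3 up to Day 85. The protocol says that this review is not about escalation but feeds the decision to open Cohort 4.

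Two further sentences in 3.1.3 bear on the point. For a suspected thromboembolic event, "the DEC will re-assess the event when complete clinical/laboratory information is provided by the study site". For restart, the text begins "If the DEC suspends the dose escalation and subsequently decides to resume dosing at the same or higher doses" and then requires regulatory and ethics committee approval before dosing.

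**The concern.** A stopping criterion works only if the action it triggers can still be taken. In Cohorts 1 and 2, suspending escalation holds back the next dose level. In Cohort 4 there is no next level, so a site or sponsor following the text would evaluate the event while randomization and two-weekly infusions continued in the rest of the cohort.

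Section 1.6 presents this suspension as the response to a thromboembolic event, the harm that halted an earlier Fc-enabled anti-CD40L antibody (Section 1.1.1). Amendment 1 extended it to suspected events on a US FDA recommendation, "such that dose escalation will be suspended even in the case of a suspected thromboembolic event, until additional data allow an informed diagnosis" (Section 9). The infection criterion has the same gap. Section 1.3 reports an opportunistic fungal infection in the 6-month IV monkey study, which set no IV NOAEL. Amendment 3 edited both 1.6 and 3.1.3 to add Cohort 4 but did not give the criteria an action that works there.

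**Working it through.** **Size of the affected group.** Inputs are from Protocol 3.1.1.
- Active: 8 + 10 + 12 + 10 = 40. Placebo: 2 + 4 + 4 + 4 = 14. Total: 40 + 14 = 54, which reproduces the maximum in 4.1.1.
- Cohort 4: 10 active and 4 placebo, which matches the 5:2 ratio. At 7 doses each, planned active infusions are 10 × 7 = 70. With placebo the cohort has 14 × 7 = 98.

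**What the suspension can hold, by cohort (3.1.3).**

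| Cohort | Dose | Next escalation step | Scheduled DEC review of its data |
|---|---|---|---|
| 1 | 75 mg | Cohort 2 | first, second and third |
| 2 | 500 mg | Cohort 3 | second and third |
| 3 | 1500 mg | none, but its data inform the opening of Cohort 4 | third, to Day 85 |
| 4 | 1000 mg | none | none |

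**Can the criteria be met in Cohort 4?** Yes. The thromboembolic criterion needs one MEDI4920 subject and runs through follow-up. The two-subject criteria count within any single cohort. None is limited to Cohorts 1 to 3.

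**Is a hold stated elsewhere?**
- 3.1.3, restart clause: resuming at the same dose makes sense only if dosing at that dose had stopped. But the clause opens with the DEC having suspended escalation, which read literally cannot happen in Cohort 4. The approval requirement may therefore fail there too.
- 4.1.6 stops dosing only in the affected subject. Its thromboembolic item is limited to serious or severe events, while 3.1.3 covers any confirmed or suspected event.
- 3.1.2 staggers dosing within each cohort so that safety can be reviewed, but gives no group size, interval, reviewer or stop criterion.
- 4.4 lets the sponsor suspend the study and requires approval before a restart after a safety suspension. The decision is discretionary and has no event threshold.
- The SAP text supplied contains no stopping rule.

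**Why Cohort 4 is the part to change.** Section 3.2.1 states that the 1000 mg cohort was chosen after review of Cohort 3 data through Day 85, which is the seventh and last dosing day (Table 3.1.2-1). Cohort 3 dosing was therefore complete before Amendment 3.

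**The case against.** The strongest reply is that the wording is loose but control is not absent. The restart clause shows that the authors had a dosing hold in mind. SAEs reach the sponsor within 24 hours (5.5). AESIs are under ongoing surveillance, with instructions in a Safety Handling Plan that is not among the documents (5.3). Subject-level stopping, staggering and 4.4 all apply in Cohort 4. The dose is below one already given for 12 weeks, and the molecule lacks Fc. Scaling the protocol's 65-fold margin at 75 mg gives 65 × 75/1500 = 3.25 at 1500 mg (protocol: about 3) and 65 × 75/1000 = 4.9 at 1000 mg.

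Much of this stands. The risk may be low, and discretionary control exists. What it does not supply is the automatic response that 1.6 and 3.1.3 offer as the safeguard. An implied hold leaves sites and sponsor free to read the rule in opposite ways when an event occurs.

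A second objection concerns the remedy. The criteria count subjects dosed with MEDI4920, but the DEC reviews blinded data, and the sponsor stays blinded to Cohort 4 until its Day 85 analysis (4.6.4). The two-subject criterion also counts any SAE, whatever its cause. A bare dosing hold could stop the cohort for two unrelated SAEs until regulators approve a restart. This is correct, and the fix has to deal with it.

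**Conclusion.** The point holds for Cohort 4: 10 active subjects and 70 planned active infusions have no pre-specified, event-triggered pause at cohort level. It should be corrected, because the sponsor's own criterion cannot do there what 1.6 says it is for. The conclusion assumes that no unseen document, such as the Safety Handling Plan, orders such a hold.

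A reader might infer more than the documents support:
- That the criteria have no effect in Cohort 4. Evaluation still applies, as does DEC re-assessment of suspected thromboembolic events.
- That Cohort 3 belongs in the count. It also had no later escalation step, but its data went to the third DEC review and into the decision to open Cohort 4, and its dosing was finished by Amendment 3.
- That a regulator asked for a dosing hold. Section 9 records only that suspected events were added to the escalation rule and that the two-subject threshold was tightened from three.
- That harm is likely. The documents give no event rate for this population, and the chance of an event would not measure what a pause prevents.

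**What to change.** In Protocol 3.1.3, state the following.
- If a criterion is met in any ongoing cohort, including Cohort 4, new randomization and further dosing in that cohort are paused, in addition to any suspension of escalation, until an ad hoc DEC review.
- While allocation is blinded, an event in any subject counts unless someone outside the blinded team shows that the subject received placebo.
- The DEC may resume dosing if a thromboembolic event is ruled out or considered unlikely, or if SAEs under the two-subject criterion are judged unrelated to investigational product.
- Otherwise the regulatory and ethics committee approval already in 3.1.3 is required before dosing resumes.

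Describe the three DEC meetings as scheduled meetings, with ad hoc meetings added if a criterion is met. Use matching wording in 1.6 and in the last bullets of 10.5.1 and 10.5.2.

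The cost is a short amendment, ad hoc DEC time and an unblinded person to check allocation. The sample size does not change. The downside is that some two-weekly infusions may be delayed or missed during a short pause, which affects PK and Week 12 data for those subjects. Because allocation is blinded, the pause would apply to all 14 subjects in Cohort 4.
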